Treatment for pediatric acute myeloid leukemia (AML) or myelodysplastic syndrome (MDS) involves intensive chemotherapy regimens that result in periods of profound neutropenia leaving patients susceptible to severe infectious complications. Infectious complications are the leading cause of treatment related mortality among AML and MDS patients, but there are little clinical data to inform whether management of neutropenia post AML chemotherapy should occur in an outpatient or inpatient setting.

Objectives:

The primary objective of this study is to compare the clinical effectiveness of outpatient versus inpatient management of neutropenia in children with AML or MDS receiving standard intensive AML frontline chemotherapy.

Study Design:

This is a bidirectional observational cohort study.

[figure not shown]
Setting/Participants:

Participants will be less than 19 years of age at their initial AML or MDS diagnosis receiving or having received frontline AML chemotherapy from seventeen participating pediatric hospitals across the United States (US). We anticipate that approximately 540 subjects will be evaluable for chart abstraction over the study period in order to study clinical outcomes including the occurrence of bacteremia and time to the start of the next course in the chemotherapy regimen, in relation to neutropenia management strategy.

Study Interventions and Measures:

There is no study intervention. Main outcomes include occurrences of bacteremia after completion of an AML chemotherapy course, and time from completion of one course to the next planned course of chemotherapy.

FIGURE 1: STUDY DIAGRAM

ANC= absolute neutrophil count ICU= intensive care unit

1 BACKGROUND INFORMATION AND RATIONALE

1.1 Introduction

Acute myeloid leukemia (AML) is the second most common pediatric hematologic malignancy with approximately 600 new cases per year among patients under 20 years of age. Although AML accounts for only about 20% of leukemias in children, it is responsible for more than half of pediatric leukemia deaths (1).

All pediatric patients with newly diagnosed AML receive multiple consecutive courses of intensive myelosuppressive chemotherapy aimed to attain complete remission (induction) and to prevent relapse (intensification) (2). Each regimen is followed by a period of prolonged severe neutropenia during which patients are at high risk for infection and hemorrhage. Previous reports have found that 57-80% of febrile neutropenia episodes among pediatric AML patients are compromised by at least one microbiologically documented infection (3, 4) with bacteremia constituting the most prevalent infection (5). These infectious complications remain a major cause of therapy-associated morbidity and mortality in children with AML (6, 7).

Recently published pediatric neutropenia guidelines make no specific recommendations regarding discharge from hospital after chemotherapy for AML because "there are no validated schemas for defining those patients at high-risk of developing complications of fever and neutropenia" (8). As a result, clinicians are left to decide whether to keep a child in the hospital until the neutropenia resolves (on average 35 days) or discharge a child to outpatient management within a few days of chemotherapy completion with instructions to return if symptoms of infection develop. Physicians that elect to observe patients with neutropenia in the hospital do so under the assumption that hospital observation will reduce the risk of serious infection and thereby reduce delays in starting the next course of chemotherapy. There is documented variation in practice across Children's Oncology Group (COG) institutions on inpatient versus outpatient management of neutropenia with approximately 60% of COG institutions reporting a policy to always keep patients hospitalized during severely neutropenic periods and the remaining 40% of hospitals reporting a policy of home management some or all of the time (9, 10). This variation in practice highlights the need for additional data on clinician-centered outcomes to appropriately guide the management of neutropenia in pediatric AML patients.

Myelodysplastic syndromes (MDSs) are a rare heterogenous group of hemopoietic clonal disorders characterized by ineffective hemopoiesis and frequent evolution to leukemia. Children with clinical and morphological features of MDS but with the cytogenetic features typical of AML are often treated with same intensive frontline chemotherapy used to treat AML (23). Thus, questions regarding clinician-centered and patient-centered outcomes in relation to outpatient versus inpatient management of neutropenia would apply equally to such patients.

1.2 Relevant Literature and Data

The limited literature on the clinical consequences of outpatient versus inpatient management of neutropenia in AML is focused on the experience of adult patients. Adult

patients discharged early to outpatient supportive care consistently had shorter cumulative lengths of stay than inpatients (11-18). Additionally, early discharge of adult AML patients receiving chemotherapy has been associated with fewer and shorter febrile episodes (15, 19), a better response to first line antibiotics, and shorter duration of intravenous antibiotic administration (13, 15, 18, 19). While these adult studies provide some reassurance that outpatient management may be safe and feasible they are limited as most included data from only a single institution, had very small sample sizes, or lacked an appropriate inpatient reference population. Furthermore, it is not appropriate to extrapolate these adult findings to pediatric patients as the risk profile for children may be much different.

The published literature with respect to outpatient management of neutropenia in pediatric AML is limited to a single study of only 13 patients from one hospital, which found similar rates of relapse and mortality for outpatient versus inpatient management of neutropenia (20). In our own preliminary analyses based on administrative resource utilization data from 43 free-standing children's hospitals in the US, we found that patients who were discharged early to outpatient management following AML induction and intensification chemotherapy courses incurred fewer cumulative days of hospitalization, but were frequently readmitted and had higher rates of antibiotic, vasopressor, and supplemental oxygen utilization than patients who remained inpatient during the entirety of their neutropenia. In the absence of clinical data and laboratory confirmation, it is unclear whether these observed increases in resource utilization are an accurate proxy for a greater incidence of infection or more severe infection in the early discharge patients.

In order to appropriately inform the decision for outpatient versus inpatient management of neutropenia associated with pediatric AML chemotherapy, a comprehensive study that collects pertinent clinical outcomes is necessary. Given that infectious complications are the leading cause of treatment related mortality among AML patients (22) and among MDS patients (24, 25), identifying such a neutropenia management strategy that leads to the best clinical outcomes will have a substantial impact on care of these patients.

Bacteremia, a cause of transient cardiac decline, occurs frequently during AML treatment and contributes to the development of cardiac dysfunction.(26) COG guidelines for rechallenging patients to anthracycline chemotherapy distinguish infection-associated LV systolic dysfunction (LVSD) from LVSD not associated with infection, allowing patients who experience resolution of infection-associated LVSD to receive additional anthracycline therapy. However, there are no data comparing the longitudinal trajectories of EF/SF or the impacts on subsequent cardiomyopathy and treatment outcomes for these distinct presentations of cardiotoxicity.

1.3 Compliance Statement

This study will be conducted in full accordance with all applicable Children's Hospital of Philadelphia Research Policies and Procedures and all applicable Federal and state laws and regulations including 45 CFR 46. All episodes of noncompliance will be documented.

The investigators will perform the study in accordance with this protocol and will report unanticipated problems involving risks to subjects or others in accordance with The Children's Hospital of Philadelphia IRB Policies and Procedures and all federal

requirements. Collection, recording, and reporting of data will be accurate and will ensure the privacy, health, and welfare of research subjects during and after the study.

2 STUDY OBJECTIVES

The purpose of this study is to compare the effectiveness of outpatient versus inpatient management of AML neutropenia or MDS in individuals receiving standard AML frontline chemotherapy. We plan to accomplish this through the following Objectives:

2.1 Primary Objectives

- **2.1.1** Compare the incidence of bacteremia among children with AML or MDS receiving standard intensive AML frontline chemotherapy monitored in the outpatient setting during neutropenia ("early discharge") relative to those who remain hospitalized ("inpatient").
- **2.1.2** Compare the length of time to initiation of the subsequent chemotherapy course between children with AML or MDS receiving standard intensive AML frontline chemotherapy monitored in the outpatient setting during neutropenia to similar children who remain hospitalized.

2.2 Secondary Objectives

2.2.1 Identify subpopulations based on distinct longitudinal patterns of LV ejection fraction (EF) and fractional shortening (SF) decrease and recovery and evaluate the impact of bacteremia on the longitudinal patterns of LVEF and LVSF. Compare relapse risk (RR) and OS in subgroups.

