3.3 Total Number of Study Sites/Total Number of Subjects Projected

3.3.1 Duration of Study Participation

No direct patient contact is necessary for this study; only medical record abstraction. The chart abstraction window for each participant will include the time period from the start of the first course of chemotherapy until the date of last patient contact or death.

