5 STUDY EVALUATIONS AND MEASUREMENTS

5.1 Screening and Monitoring Evaluations and Measurements

5.1.1 Medical Record Review

The following variables will be abstracted from the medical chart:

Variable Date of birth Sex Patient race/ethnicity Date of AML/MDS diagnosis Age at AML/MDS diagnosis Vital status Date of death or date of last known follow-up Location of death (in hospital or at home) AML subtype AML risk classification and cytogenetics Hospital admission start/stop dates Chemotherapy course Chemotherapy regimen and start/stop dates Course start/stop dates Clinical trial enrollment and specific protocol Documentation of deviation from planned chemotherapy course Presence/type of central line MRD post courses and dates of MRD obtained Post course remission status Daily max. fever; how was temperature taken Infections during chemotherapy courses ICU care during chemotherapy courses ANC measurements post chemotherapy Dates of ANC measurements Dates and results of microbiological cultures/PCRs onset during post chemotherapy course follow-up Mucositis by course Systematic antimicrobial prophylaxis at each course Height, weight, and body surface area at start of chemotherapy course Nutritional status/supplemental support requirements on day of chemotherapy completion Ability to practice oral hygiene Insurance status at course start (private, self-pay, public, other) English spoken? Home address Availability of working telephone Automobile/taxi voucher requirements Date of relapse Site of relapse Date of transplant Type of transplant Echocardiographic evaluations (e.g., dates, resulting measurements, measurement mode) Blood pressure and heart rate at echocardiographic evaluations Dexrazoxane administration Malignant blast percentage

| Bone marrow malignant blast percent |
|---|
| Empiric/definitive anti-infective use |
| Preferred language |
| Treatment and positive blood cultures at outside hospital (y/n) |
| Down Syndrome diagnosis |
| CNS status at the end of each course |
| Outpatient encounters (e.g., clinic/day hospital, ED) |

Some information will be retained for all screened patients to document the reasons for ineligibility. Specifically, we will be retaining information on age, leukemia diagnosis, treatment course, and whether the patient received reduced intensity chemotherapy.

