6.3.1 Analysis of Secondary Outcome of Interest

One secondary outcome of interest is LV function quantified as EF and SF over the courses of therapy and post-treatment follow-up. LVEF and LVSF trajectories will be determined by group-based latent trajectory modeling, a type of structural equation modeling which identifies distinct clusters of individuals based on development, progression, and resolution patterns pertaining to the repeated measures of a given variable. The following factors will be explored as predictors identified trajectory phenotypes: age, gender, race, ethnicity, weight group, presenting white blood cell count, and baseline EF/SF. Univariate and

multivariable mixed effects regression models will be fitted to quantify the association between bacteremia and longitudinal EF and SF measurements.

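### Relapse and OS are to be compared between EF/SF trajectory classes with nothing separating class formation from the period in which deaths occur, so OS could differ between classes when there is no true difference

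*Combined protocol and SAP*

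**What the plan says.** Section 2.2 sets the secondary objective: "Identify subpopulations based on distinct longitudinal patterns of LV ejection fraction (EF) and fractional shortening (SF) decrease and recovery", relate bacteremia to those patterns, and "Compare relapse risk (RR) and OS in subgroups".

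The second section numbered 6.3.1 (Analysis of Secondary Outcome of Interest) defines the outcome as "LV function quantified as EF and SF over the courses of therapy and post-treatment follow-up". It uses group-based latent trajectory modeling, which it describes as a method that "identifies distinct clusters of individuals based on development, progression, and resolution patterns pertaining to the repeated measures of a given variable". It then lists predictors of class membership and mixed models for bacteremia, and ends. It gives no method for the relapse and OS comparison: no time origin, landmark, cut-off for echocardiograms, class-assignment rule or joint model.

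Section 3.3.1 sets one chart abstraction window for every patient, "from the start of the first course of chemotherapy until the date of last patient contact or death". Section 5.1.1 lists echocardiogram dates and results, date of relapse, and date of death or last follow-up among the variables abstracted.

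**The concern.** A recovery class is defined by something seen late. A patient who declines and dies before recovery could have been observed has a series that fits persistent decline and decline-then-recovery almost equally well. If the classes are formed from all available echocardiograms and OS is then compared between them over the same follow-up, early deaths help decide the class as well as the outcome.

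An OS difference between recovery and persistent decline could then be reported when none exists, or a real one could be hidden or exaggerated. Section 1.2 motivates the objective by the lack of data on outcomes after different presentations of LV dysfunction, so readers would use this contrast.

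**Working it through.** **1. Stated figures.** The documents give no event count, alpha or power for this comparison, so there is no figure to reproduce. Every number below is an illustration under stated assumptions.

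**2. Why the death moves.** The probability of class k given a series is proportional to (class share) x (likelihood of the series in class k). Before recovery is visible, the two decline classes have the same likelihood, so only the shares count. With assumed shares of 25% persistent and 15% recovery, the probability of persistent decline is 25/(25 + 15) = 62.5%. Most-probable-class assignment sends all such patients to persistent decline, although 37.5% of them belong to the recovery class.

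**3. Hand calculation, no true effect.** Take 100 patients with those shares, 3-year OS of 70% in both classes, and every death before tau = 6 months (0.5 year) assigned to the larger class. The hazard is constant within year 1 and constant after it. With S the survival function and time in years:

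- Recovery class (smaller): deaths = 15 x [S(0.5) - 0.70]; person-years = 15 x [0.5 x S(0.5) + area under S from 0.5 to 3].
- Persistent class (larger): deaths = 25 x 0.30 + 15 x [1 - S(0.5)]; person-years = 25 x (area under S from 0 to 3) + 15 x [area under S from 0 to 0.5, minus 0.5 x S(0.5)].

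| 12-month mortality | S(0.5) | Recovery: deaths / person-years | Persistent: deaths / person-years | Rate ratio |
|---|---|---|---|---|
| 4% | 0.980 | 4.197 / 39.32 | 7.803 / 65.73 | 0.90 |
| 11.2% (constant hazard, 1 - 0.70^(1/3)) | 0.942 | 3.634 / 37.64 | 8.366 / 63.30 | 0.73 |
| 18% | 0.906 | 3.083 / 36.01 | 8.917 / 60.94 | 0.59 |

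The true ratio is 1 in each row. If recovery is the larger class, the error runs the other way.

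**4. Simulation.** Setup: n = 540; three classes (stable, persistent decline, decline then recovery); EF falling 15 points by month 4.5; residual SD 5; echocardiograms at 0, 1.5, 3, 4.5, 6, 9, 12, 18, 24 and 36 months until death; recovery over months 4.5-9 or 6-12; classes fitted by EM started at the true values, which favours the method; most-probable-class assignment; nominal 5% log-rank test.

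- Constant hazard, 3-year OS 60-80%, 24 scenarios of 2,000 trials. The recovered/persistent ratio was 0.72-0.82 with recovery smaller (15% v 25%; 9-25% rejection), 1.23-1.48 with recovery larger (20% v 10% or 35% v 15%; 6-36%), and 0.99-1.01 with equal classes (5-11%).
- 3-year OS 70%, unequal classes, mortality timing varied. The ratio was 0.88-1.12 (6-7% rejection) at 4% 12-month mortality; 0.70 or 1.43-1.46 (17-29%) at 11%; and as far out as 0.56 or 2.04 (29-62%) at 18%.
- A second simulation used another schedule, recovery timing and censoring, with 600 trials per scenario. Its persistent/recovered hazard ratios of 0.72-0.79 (recovery larger) and 1.27-1.33 (recovery smaller) invert to 1/0.79 to 1/0.72 = 1.27-1.39 and 1/1.33 to 1/1.27 = 0.75-0.79. Rejection with unequal classes was 6.3-33.0%. Using the true class it was 4.2-6.8%, so the error comes from class assignment.

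**5. Alternatives.** With no true effect and constant hazard, a 12-month landmark gave ratios of 0.97-1.02 and 4.2-5.8% rejection; with mortality timing varied, ratios stayed near 1 with about 3-8% rejection. Class-probability weighting over full follow-up gave 0.985-1.011 and 2.9-5.3%. With a true ratio of 0.50:

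| Method | Estimated ratio |
|---|---|
| Most probable class, recovery smaller | 0.43-0.48 |
| Most probable class, recovery larger | 0.70-0.88 |
| Most probable class, equal classes | 0.61-0.71 |
| Class-probability weighting | 0.61-0.67 |
| 12-month landmark | 0.51-0.55 |

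**6. Relapse, no true effect.** If echocardiograms continue after relapse, the ratio was 0.92-1.11 with 4.0-7.5% rejection. If they stop at relapse, it was 0.72-0.80 or 1.25-1.49 with 11-36% (unequal classes).

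**The case against.** The strongest reply is that the plan states no method for this comparison, so a bias is being attributed to an analysis nobody has described. Most-probable-class assignment is assumed, not planned. The window in section 3.3.1 governs chart abstraction, not the OS analysis, and a landmark would contradict nothing in the text. Section 1.2 also allows another meaning of subgroups, infection-associated versus other LV dysfunction, when it speaks of "impacts on subsequent cardiomyopathy and treatment outcomes for these distinct presentations of cardiotoxicity"; the figures above do not apply to that reading.

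The size is also uncertain. Late mortality largely removes the problem, as the 4% row shows, and the documents give no mortality timing. Even 540 is borrowed: sections 3.3.2 and 6.4 give it as the early-discharge-eligible count for the primary comparison, out of about 600 identified, and the number with usable serial echocardiograms is unknown. A 12-month landmark has no basis in the documents either.

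All of this stands as a limit on size and strength. It does not remove the point. Section 2.2 most naturally means the trajectory classes, since it names them in the preceding sentence. Section 6.3.1 as written feeds post-treatment echocardiograms into those classes, and no provision protects the later comparison.

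A reader might infer that recovery will always look better because recovered patients must have survived. The calculations do not support that: the direction follows class size, and with equal classes the ratio is near 1.

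**Conclusion.** The point holds as a conditional one. Followed as written, the plan can make class membership depend on survival. If patients are put in their most probable class, OS can then differ between the recovery and persistent-decline classes with no true difference. With unequal classes and 3-year OS of 70%, the distortion is slight at 4% 12-month mortality, material at 11% and large at 18%. Which of these applies cannot be told from the documents, and the fitted class sizes would show the direction of the error but not its amount.

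A reader might go further and take the simulated rejection rates as rates for this study, or assume that relapse is distorted equally. Neither is supported. The inputs are assumed, and relapse is materially affected only if echocardiograms stop at relapse. The documents do not say that they do, and abstraction runs on to last contact or death.

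This is a cheap improvement to a secondary objective. The bacteremia and time-to-next-course endpoints are unaffected.

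**What to change.** In the secondary-outcome part of section 6.3.1:

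- State whether subgroups means the trajectory classes. If it does, apply the rest.
- Prespecify one landmark, chosen from the observed echocardiogram schedule and late enough for recovery to be seen. Twelve months from the start of the first course is an example only. In the simulation a 6-month landmark gave a usable recovery class in 76-87% of trials when recovery began at month 4.5, and in none when it began at month 6.
- Form classes only from echocardiograms up to the landmark. Compare OS from the landmark in patients alive then. Compare relapse in those alive and relapse-free, with death as a competing event.
- State the class-assignment rule and whether echocardiograms after relapse are used.
- As a sensitivity analysis over full follow-up, report a class-probability-weighted comparison with robust standard errors or a joint trajectory-survival model. Note that weighting attenuates a true effect.

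**Cost.** No new data are needed, because the dates are already abstracted under section 5.1.1. The work is SAP wording plus one added analysis; a joint model would take more.

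The landmark drops early events. Under constant hazard, a 12-month landmark loses (1 - S^(1/3))/(1 - S) of 36-month deaths, where S is 3-year OS: 39.1%, 37.4% and 35.8% for S = 0.6, 0.7 and 0.8. At n = 540 and OS 70%, that is 540 x 0.30 = 162 deaths falling to 162 x (1 - 0.374) = about 101. In the simulation about 40% of relapses were lost (206 to 123). Losses are greater if events fall early. The result is conditional on surviving to the landmark, and recovery after it cannot define a class. Simulated power for a true ratio of 0.50 was 38-71% with the landmark and 42-75% with weighting.
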